## **Executive summary**

The proposed research is a proof of concept trial to establish how effective a high intensity hand hygiene intervention after deworming can be in reducing both intensity and prevalence of selected helminthic infections among primary school students.

This work will be conducted in the Kagera Region of Tanzania, NW-Tanzania. Surveys conducted in this populous area have shown a very high prevalence of infection with *Ascaris lumbricoides* and *Trichuris trichiura*, ranging from18% to more than 50% (Brooker 2009; Siza 2015), particularly among children aged 6 – 12 years, indicating both the urgent need for an effective intervention and also the suitability of this environment for the proposed study.

The proposed behaviour change intervention will be a combination intervention package comprising of the following components: teacher-led health education in primary schools, low-cost structural improvements with respect to water supply and sanitation, nudges to increase students intention to wash hands after defecation, screening of students for current worm infection combined with feedback of results to parents and health information given to students' parents. The intervention will use a health promotion strategy that aims to generate emotional drivers similar to that validated in the SuperAmma study (Biran 2014) which had shown substantial increases in hand-washing behaviour in India. This intervention will be primarily school-based, but will involve children's parents and guardians. The exact operational details of the above intervention components will be informed through

qualitative (formative) research that is currently being conducted at 3 pilot schools and communities in Kagera Region (under a separate protocol with separate ethical clearance).

The efficacy of the intervention will be tested through an open-label clusterrandomised controlled trial, with primary schools being the unit of randomisation, involving students recruited from intervention and control schools. The primary outcome will be the prevalence of infection with ascaridiasis and trichuriasis following deworming in both intervention and control schools. Secondary outcomes will include self-reported hand-washing behaviour both at home and in schools, the prevalence of worm eggs retrieved from hands in a subgroup of pupils, and the prevalence of hookworm infection.

# Background

Chronic diarrhoea and helminthic infections, especially soil transmitted helminths (STH), are frequent infections in childhood, and are strongly associated with malnutrition, poor child development and cognitive performance. Both diarrhoea and helminthic infections have a strong association with poor access to water supply, sanitation and hygiene. Malnutrition is responsible for 45% of children's deaths in low and middle income countries, and also has long term consequences such as: short adult height and associated complications during delivery, low birth weight, impaired cognitive, motor and social development, and reduced economic productivity.

Control of STH has largely depended on the administration of anthelmintic drugs, though a recent systematic review has shown that the use of school based deworming programmes had little to no impact on child development and cognitive performance (Taylor-Robinson 2012). Reinfection is often rapid, and for Ascaris infection sometimes reaches pre-treatment levels within six months post-treatment (Yap 2013), as the root causes of transmission have not been addressed. Open defecation has been shown to have a strong association with all STH infections (Ziegelbauer 2012). Although the results of recently published randomised controlled trials on the impact of sanitation interventions on STH in India have shown that sanitation programmes can increase the coverage of latrines, actual use of latrines remains low, with especially men and children still practicing open defecation (Patil 2014, Clasen 2014).

STH have a low infective dose, where a single egg can cause an infection, and especially Ascaris eggs can survive and remain infective for several months in the environment (Nordin 2009), and are particularly sticky (Brownell 2007). They are predominantly found in soil, but also on vegetables, especially in areas where human faeces or wastewater are used as fertilizer (Ensink 2008, Do 2007). People pick up Ascaris and trichuris infections when they ingest these eggs after they have matured in the environment by eating raw, unwashed vegetables or by not washing their hands after handling contaminated soil which is thought to be a common transmission route for children (Ziegelbauer 2012).The exact role of hands in the transmission of eggs is unclear, as a systematic review on the impact of hand washing with soap and ascariasis remained inconclusive (Fung and Cairncross 2009). However, results from a more recently completed randomised controlled trial in China found that the promotion of hand washing with soap in schools resulted in a 50% reduction in STH prevalence (Bieri 2013). A pilot study to test a method developed under SHARE phase 1 to quantify eggs on hands found 34% of hands of farmers who used fresh excreta as a fertilizer positive for STH eggs (Gulliver 2014), while a study among school children found a prevalence of about 20% (Cranston 2015).

Deworming campaigns remain a cost-effective way to reduce the burden of STHs (Clarke 2017), but as deworming does not target the root causes of STH and reinfection occurs rapidly, an integrated approach that combines sustainable hygiene behaviour change with deworming could prove an effective way to control STH infections.

The proposed study aims to establish whether the effect of routine deworming campaigns can be enhanced and sustained by combining it with an appropriate Water, Sanitation and Hygiene (WASH) behaviour change intervention.

In preparation of our protocol we took careful note of the findings from the large scale 'SWASH project' intervention programme that has been conducted at schools in Kenya (Freeman 2013; Freeman 2014; Caruso 2014; Saboori 2013; Greene 2012). This programme focused on improving the availability of clean toilets and soap at schools and was combined with some hygiene promotion, and was successful in reducing the prevalence of ascariasis by about 50% and Ascaris egg work load by nearly 70% (Freeman 2013).

There are a number of differences between the work in Kenya and the work we are proposing here. Different from our proposed intervention, the SWASH project did not include an educational behaviour change intervention per se, it did not aim at changing WASH behaviour both *at home and at school*, it did not involve parents and guardians, and there is also evidence from the SWASH publications that water has not been sufficiently available even at those schools that had water 'within reach'. Importantly, the creation of a strong *emotional motivation* to wash hands at key times is the central component of our proposed intervention, and in this respect goes substantially beyond the intervention efforts in the Kenyan studies.

One important observation from the SWASH programme was the total lack of consumables at schools for anal cleansing after defecation, mainly for cost reasons (poverty). We are aware that this is also a problem at primary schools in Tanzania, and may affect our proposed trial. It can be argued that under such circumstances open defecation in an area that at least provides access to plant material may be better than using an insufficiently equipped and dirty latrine. However, we argue that cleansing of the anal area by hands or with inappropriate materials as often used (e.g. stones, old garbage paper) *but followed by careful hand-washing*, whilst less than ideal, may go a long way to reduce the risk of faecal-oral transmission, both with respect to bacteria and helminths.

# Aims and objectives

The overall aim of the proposed cluster-randomised controlled trial is to assess the effectiveness of a behaviour intervention package for the promotion of hand washing with water and soap, among school aged children in NW Tanzania in reducing both the prevalence and intensity of *Ascaris lumbricoides* and *Trichuris trichiura* infections in these children. Through this work, we aim to lay the foundation for a future (cost-)effectiveness study of the intervention to be conducted within the context of the ongoing school-based national deworming programme in Tanzania.

## **Specific objectives**

- 1. To introduce a scalable, school-based combination intervention to promote hand-washing with water and soap at key times during the day among school aged children (6-12 years) in NW Tanzania.
- 2. To assess the effectiveness of this intervention in changing hand-washing behaviour in the study population.
- 3. To assess the effectiveness of this intervention in reducing the prevalence and intensity of *Ascaris lumbricoides* and *Trichuris trichiura* infections in the study population.
- 4. To explore the costs and the cost-effectiveness of the intervention in order to inform the Tanzanian government with respect to the possible integration of the intervention into the national STH control efforts.

# Methods

To achieve these objectives we propose to conduct a study in which a high intensity hygiene behaviour change programme will be implemented in order to determine 'the maximum' reduction in prevalence and intensity of infection that hand-washing with soap can achieve, after routine deworming as provided by the ongoing Tanzanian national programme for the control of neglected tropical diseases (NTDs). We propose a cluster-randomised controlled trial in 16 schools in Kagera Region of NW Tanzania.

## Study Area

Kagera Region is the large area situated between the shores of Lake Victoria in NW Tanzania, and the borders of Tanzania to Uganda and Rwanda. The region has a population of about 2.46 million people (NBS 2012). The capital city of the region is Bukoba with about 300,000 inhabitants. The region comprises seven districts, each with sizable district towns, of which Bukoba, Muleba and Karagwe are the largest. The main economic activity in the region is agriculture, with farmers growing a range of food crops, including coffee and tea for export markets. Other activities include fishing and industrial processing of fish for export. The continuing urbanisation of the region's towns, coupled with high population growth and often inadequate infrastructure, contributes to the existing high burden of infectious diseases such as malaria, STH, respiratory tract infections, diarrhoea, and HIV/AIDS, and an emerging epidemic of non-communicable diseases.

All major villages of the region have primary schools, and the total number of primary schools in the region is about 800. The schooling rate is high, exceeding 90% in urban areas. The prevalence of ascariasis among school children has been estimated to exceed 25% in most places (Brooker 2009). In a recent still unpublished survey conducted by our team among 2000 students from 34 primary schools in Kagera, the prevalence of ascariasis and trichuriasis ranged from 0 - 71%, exceeding 25% in most schools ([name] – personal communication).

### Intervention design

Design of the intervention will draw on experience from India (Biran 2014), Kenya (Freeman 2014, Saboori 2013) and Bangladesh (Dreibelbis 2016) as well as recent successful behaviour change interventions in Zambia and ongoing work in Nigeria (unpublished).

### Underlying principles

- 1. The intervention will be mainly school based, but will involve students' parents or guardians to ensure their support.
- 2. The intervention will be intensive, but affordable and feasible within the public primary school education system allowing it to be replicated and upscaled in other primary schools in Tanzania, if shown to be effective.
- 3. The behaviour change intervention will combine emotional drivers (in line with current thinking on behaviour change) and structural facilitators ('nudging'), with classical health educational messages.
- 4. Practical details of this combination intervention will be adapted to the cultural context in Tanzania, and will be designed based on qualitative (formative) research currently conducted at pilot schools in Kagera.
- 5. Deworming treatment with helminths will be provided in all primary schools involved in this trial, as part of the national deworming programme. All participating schools will have a reliable water supply and hand washing points. Schools in the intervention arm of the trial will, in addition, receive the proposed behaviour change intervention to promote hand washing with water and soap. Deworming will be timed so that it is executed just after the behaviour change intervention has started in intervention schools. Timing it in this way ensures that the intervention is in place in intervention schools at the time of the deworming exercise, and that potential infections would occur in-spite of the intervention (and not because the intervention is not yet up and running).

#### **Deworminq**

Deworming campaigns are usually conducted at regular intervals of 12 months under the auspices of the national neglected tropical diseases (NTD) control programme, Ministry of Health, Community Development, Gender, Elderly, and Children of the United Republic of Tanzania. In this trial, deworming will be performed in both intervention and control schools by the national NTD control programme if timing permits, or by research staff according to guidelines of the Ministry of Health to ensure that deworming and the hand-washing intervention are synchronised (see Figure 2). Treatment will be with Albendazole according to guidelines (400 mg, single dose).

### Intervention components

Classes 1 to 6 of the participating primary schools will receive the intervention; and the majority of the children in these classes are expected to fall into the age-band of 6 - 12 years. The intervention will consist of the following components:

- 1. *Initial worm infection survey in intervention schools:* To generate maximum parental support for the intervention among students from schools in the intervention arm, we will conduct an initial screening for STH in these students, using the Kato-Katz methods.
- 2. Parents' and guardians' meeting: Following the survey, parents and guardians of students from the same class will be invited for a meeting at the school. On this occasion, the results about the infection of their individual children will be given to the respective parents, provided in individual (confidential) envelopes. Dedicated teachers, supported by project staff, will explain the meaning of the results to the audience. They will provide information on the potential consequences of worm infections for the health and development of children, briefly explain routes of infection and how to reduce risk of infection through hand-washing behaviour at key times. The purpose of this intervention component will be to raise personal emotional concern among parents and guardians, establishing the desire to improve hygiene behaviour in the home and to provide parental support to the proposed class-room based behaviourchange education described under point 3 below. The aim is to improve hygiene behaviour in the family in general, and among children both at home and at school. Messages will focus on hand-washing behaviours at key times, but the need for clean food and water will also be discussed.

This strategy has been employed with high and statistically significant effect in the Ukerewe District of Mwanza Region from 1993 – 1996, in order to promote hygiene and latrine building (personal communication, [name], HESAWA SIDA Project). Unfortunately this experience has not been published as the PI died soon after the end of the intervention project.

3. Class-room based health education: In each school we will train two interested teachers who will over time provide up to 3 teacher-led sessions of up to 2 x 1 hour to each class about personal hygiene, during the course of one school year. In this effort they will be supported by project staff. All classes 1 to 6 of the participating primary schools will receive the intervention; and the majority of the children in these classes are expected to fall into the age-band of 6 - 12 years. The sessions will (i) focus on basic essential health information on STH, adapted to the mean age level of each respective class; (ii) use educational

[figure not shown]
material to generate behaviour change intentions using emotional drivers(feelings of disgust about faecal hand and food contamination), and (iii) offer solutions through demonstration of hand-washing which will be embedded in hygiene messages.

Sessions will be delivered using health information and the education materials described below under point 5. The sessions will be delivered according to the schedule shown in Figure 2: the first intervention session will be delivered about 4 weeks after the initial worm infection survey described above and about 2 weeks after the parents' meeting, and will be timed to occur about 2 weeks prior to the deworming campaign. A re-enforcement session will be provided within 2 weeks after the deworming campaign. A second re-enforcement session will be conducted after about a further 6 months (Figure 2). During these intervention sessions, correct hand-washing behaviour with water and soap will be demonstrated and practiced.

- 4. Hand washing areas will be equipped with soap bars or with soap water solutions (Saboori 2013), depending on findings from the formative phase of the project (see below).
- 5. *Educational materials for use during school sessions:* These will comprise pictorial displays. The material will aim to both provide information and raise the feeling of disgust among children with respect to the possible contamination of hands and food by faecal materials as described under point 3. The materials may be enhanced through storytelling and role-plays, depending on the results from the formative research phase (see below).
- 6. Information leaflets for parents and guardians: These will be designed to reinforce messages provided at the parents' and guardians meeting (see point 2 above), and to reach parents who did not attend this initial meeting. The leaflets will be written in Kiswahili. Children will be asked to return the lower part of the leaflet with a signature by their parent confirming that the leaflet has been seen.
- 7. *Nudging:* Nudges are environmental cues engaging unconscious decision-making processes to prompt behaviour change (Dreibelbis 2016). Typical nudges comprise footprints on footpaths painted in bright colours that aim to guide students to handwashing stations (Figure 1). They can also include handprints painted at stations. The potential use of these nudges and their exact design will depend on the outcome of the formative research (see below).

#### Figure 2 Relative timing of intervention events, surveys, and deworming campaign

#### Development and piloting of the intervention

The trial is preceded by a preparatory phase to conduct qualitative (formative) research in three schools of Kagera region with the aim to pilot details of the intervention package described above as components 1 - 7. These schools are different from those to be recruited for the trial. This preparatory work is being conducted under a separate protocol (with separate ethical clearance) and is being performed by two social scientists under the supervision of a senior WASH experienced anthropologist and of the PI of the main trial, in close collaboration with local authorities of the Ministry of Health and Social Welfare, and the Ministry of Education in Kagera region.

## Activities in the control arm

There will be no WASH promotion related intervention activities in the control arm. The deworming campaign will be conducted in both arms of the trial as depicted in Figure 2 above. However, students from schools in the control arm will have access to water and devices to wash hands like those in the intervention arm. They will not receive (additional) soap through the intervention project (as this would be an intervention in itself that may change behaviour and therefore possibly dilute the measurable intervention effect between arms).

### **Evaluation of the intervention**

#### Overview

The intervention will be evaluated through a cluster randomised controlled trial. Sixteen primary schools will be randomised to receiving the above intervention package (N=8) or to be in the control arm (N=8).

Whilst the intervention will be delivered to all classes 1 - 6 of the schools randomised to the intervention arm, a random selection of classes will be recruited for the evaluation. For the evaluation, we will select an equal number of classes in both arms, and the random selection will be restricted so that selected classes represent comparable age bands (to avoid that by chance there would be more 'younger' classes in one of the trial arms than in the other). The target group will be children aged 6 - 12 years, but all children in the participating classes will be enrolled, including those that may fall outside of this age band.

The evaluation will involve two cross-sectional surveys: a baseline survey (conducted just after the deworming campaign in both arms of the trial, and just after the intervention has been started in the intervention arm); and an endline survey to be conducted about 12 months after the baseline survey in each respective school (Figure 2).

#### Baseline and endline surveys

The baseline survey has three objectives: (i) to confirm whether the deworming campaign was successful, (ii) to document any baseline differences in STH prevalence between arms in order to facilitate the analysis and interpretation of trial results, and (iii) to identify specific students in schools from both arms who are still infected. These students will be treated again. The aim is to ideally eradicate STH infections in both arms so that for the purpose of the trial, infections found at the endline survey are more likely to be reinfections, and differences between infection prevalences in the two arms may be attributed to the intervention in the intervention arm. For this reason, the initial introduction of the intervention in intervention schools will be timed to occur just before the deworming campaign (so that the risk of spontaneous reinfection is reduced – see Figure 2).

## Outcomes

The primary outcome will be the combined prevalence of ascariasis and trichuriasis in students' stool samples in both intervention and control schools determined at about 12 months after initial deworming in both intervention and control schools.

Secondary outcomes will include

- (i) hand-washing behaviour in schools (reported and observed) and at home (reported only)
- (ii) intensity of ascariasis and trichuriasis infections at baseline and 12 months after deworming
- (iii) levels of hand contamination with worm eggs and E. coli bacteria at 12 months after deworming

(iv) prevalence and intensity of hookworm infection at baseline and at 12 months after deworming

#### Sample size considerations

With respect to the primary outcome, the expected combined prevalence for Trichuris and Ascaris infection in school children in study schools will be about 30%. In the absence of the hand-washing intervention, the prevalence is assumed to reach original levels within one year after deworming. The intervention is expected to reduce this by at least 40%. Table 1 shows the different numbers of clusters (schools) required per arm for different scenarios. The scenarios differ with respect to the number of students per school, the size of the intervention effects, and the intercluster coefficient of variation (k). We will aim to enrol a total of 3200 pupils from a total of 16 primary schools (8 to be allocated randomly to each trial arm). This sample size will provide at least 80% power to detect an intervention effect of at least 40%, assuming a between-cluster coefficient of variation of 0.3 (Table 1). If the baseline prevalence is indeed about 30% and the reduction of prevalence during the endline survey about 50%, this sample will provide about 95% power to detect this effect size (Hayes and Bennett).

Type-1 error	Power	Prevalence in comparison arm	Prevalence in intervention arm	Nu. of students per school	Coefficient of variation k	Nu. of schools per arm	Total nu. of participants
0,95	0,8	40.00%	30.00%	300	0.25	15	6000
0,95	0,8	40.00%	25.00%	300	0.3	8	3200
0,95	0,8	40.00%	20.00%	200	0.3	5	2000
0,95	0,8	30.00%	20.00%	300	0.25	9	3600
0,95	0,8	30.00%	18.00%	200	0.3	8	3200
0,95	0,8	30.00%	15.00%	200	0.3	6	2400
0,95	0,8	20.00%	15.00%	300	0.3	22	8800
0,95	0,8	20.00%	13.00%	200	0.3	12	4800
0,95	0,8	20.00%	10.00%	200	0.3	5	2000
0,95	0,95	30.00%	15.00%	200	0.3	8	3200

#### Table 1

When selecting participants within schools, we will aim for a gender balance of 1:1 overall. In each school we expect to recruit about 3 - 5 classes of pupils in whom the majority of pupils is aged between 8 and 12 years, aiming for 200 students per school, and an even distribution of age groups within the target age band. All assenting students in a selected class will be enrolled, even if their number exceeds the target, and if some students would fall outside of the target age.

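### The stated 80% and 95% power rest on an unsourced k = 0.3, which looks low against the team's own 34-school survey; power should be restated at the k from that survey

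*Protocol*

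**What the plan says.** Under Sample size considerations the protocol states that "the expected combined prevalence for Trichuris and Ascaris infection in school children in study schools will be about 30" per cent and that, without the intervention, "the prevalence is assumed to reach original levels within one year after deworming". On the effect it says "The intervention is expected to reduce this by at least 40" per cent. With 8 schools per arm and 200 pupils per school it concludes: "This sample size will provide at least 80% power to detect an intervention effect of at least 40%, assuming a between-cluster coefficient of variation"; the value assumed for k is 0.3. It adds that with "the reduction of prevalence during the endline survey about 50%, this sample will provide about 95% power to detect this effect size".

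Table 1 uses only k = 0.25 and k = 0.3, and neither value is given a source.

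Under Study Area the protocol describes relevant data: "In a recent still unpublished survey conducted by our team among 2000 students from 34 primary schools in Kagera", where "the prevalence of ascariasis and trichuriasis ranged from 0 - 71%, exceeding 25% in most schools". It reports no mean, standard deviation or k from that survey, and the sample size section does not refer to it.

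The only restriction stated for trial schools is reliable water and hand-washing points (Underlying principles, item 5). No prevalence criterion, stratification or matching is stated.

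**The concern.** At a mean prevalence of 30%, k = 0.3 is a between-school standard deviation of 0.3 × 30 = 9 percentage points. On a normal approximation about 95% of schools would then lie within 30 ± 1.96 × 9, that is 12% to 48%. A survey in the same region that runs from 0% to 71% suggests a wider spread. Because the protocol assumes control schools return to their original levels within a year, the natural spread between schools bears directly on the endline comparison.

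The choice of k matters more here than any other input. With 200 pupils per school, between-school variation makes up about 86% of the variance of the comparison at k = 0.3, so enrolling more pupils per school cannot compensate. There is also no slack: the formula asks for 7.98 schools per arm and 8 are planned.

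The Study Limitations section wants the reasons for a null result to be separable: an intervention that failed, or other sources of infection. If k is well above 0.3, low power is a further explanation, and the protocol does not mention it.

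**Working it through.** **Inputs.** From Sample size considerations and Table 1: p0 = 0.30; p1 = 0.18 (40% reduction) or 0.15 (50% reduction); m = 200 pupils per school; c = 8 schools per arm; k = 0.3. From Study Area: 34 schools, 2000 pupils (2000/34 ≈ 59 per school), range 0 to 71%. Assumed: two-sided 5% test (the type-1 error column prints 0,95 and sidedness is not stated), equal numbers per surveyed school, and a survey mean of 30% to 40%.

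**Formula (Hayes–Bennett, unmatched).** V = p0(1−p0)/m + p1(1−p1)/m + k²(p0² + p1²). Then c = 1 + (z₀.₉₇₅ + z_power)² V/(p0−p1)², and power = Φ(√[(c−1)(p0−p1)²/V] − 1.96).

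**Step 1: the plan's own figures.**
- 30% to 18%: V = 0.00105 + 0.000738 + 0.09 × 0.1224 = 0.012804. c = 1 + 7.849 × 0.012804/0.0144 = 7.98. Power with 8 per arm is 80.1% (79.6% by non-central t, 14 df). Between-school share: 0.011016/0.012804 = 86%.
- 30% to 15%: V = 0.00105 + 0.0006375 + 0.09 × 0.1125 = 0.0118125. c = 1 + 12.995 × 0.0118125/0.0225 = 7.82. Power is 95.5% (95.2% by non-central t).

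Both statements reproduce at k = 0.3.

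**Step 2: what k the survey range suggests.** The expected range of 34 normal values is 4.19 SD, so SD ≈ 0.71/4.19 = 0.169. Subtract binomial sampling variance, mean × (1 − mean)/59, and divide by the mean:

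| Assumed mean | k before subtraction | SD after subtraction | k net |
|---|---|---|---|
| 30% | 0.56 | 0.159 | 0.53 |
| 35% | 0.48 | 0.158 | 0.45 |
| 40% | 0.42 | 0.157 | 0.39 |

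**Step 3: how well k = 0.3 fits.** In a beta-binomial simulation of 34 schools with 59 pupils each and k = 0.3, the average range is 44 points at mean 30%. A range of 70 points or more occurs in fewer than 0.1% of draws at mean 30% and in about 2% at mean 40%.

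**Step 4: power over k, with 8 schools per arm and 200 pupils each.** For example, at k = 0.40, V = 0.001788 + 0.16 × 0.1224 = 0.021372; √(7 × 0.0144/0.021372) = 2.172; Φ(2.172 − 1.96) = 58%.

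| k | Power, 30% to 18% | Power, 30% to 15% | Reduction detectable at 80% power | Schools per arm for 80% power, 30% to 18% |
|---|---|---|---|---|
| 0.30 | 80% | 95% | 40% | 8 |
| 0.35 | 69% | 89% | 45% | 11 |
| 0.40 | 58% | 81% | 50% | 13 |
| 0.45 | 50% | 72% | 54% | 16 |
| 0.50 | 42% | 63% | 59% | 19 |
| 0.53 | 39% | 59% | 62% | 21 |

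**The case against.** The strongest reply is that a range is set by two schools. Suppose one school is at 0%, one is at 71%, and the other 32 centre on 33% with an observed SD of 8 points. The mean is then 33%, k is 0.35 before and 0.30 after removing sampling error, and this is consistent with everything the protocol reports about the survey. This stands. A reader might infer that the survey contradicts k = 0.3, and the documents do not support that. The case does need two isolated extremes. If the other 32 schools centre on 30% with an observed SD of 9 points, the overall SD is √[(31 × 0.09² + 0.303² + 0.407²)/33] ≈ 0.124, so k is about 0.41 before and 0.36 after removing sampling error.

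Nor do the range-based values of k fix the answer. In the same simulation, a school at 0% together with one at 70% or more occurs in about 6% of draws at mean 30% and k = 0.53, 2% at mean 35% and k = 0.45, and 1% at mean 40% and k = 0.39. The normal-range estimate and the beta-binomial model therefore do not agree closely, and the actual numbers of pupils per school are not given.

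The survey may also not represent the trial. Schools with reliable water may be more alike than 34 schools across Kagera. The wording leaves open whether 0 to 71% is the combined prevalence or covers the two species separately. The k that matters is at endline, after deworming and re-treatment, although the protocol does assume a return to original levels. These points make k uncertain; they do not supply a source for 0.3.

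Finally, this is a proof-of-concept trial, and the protocol already plans to explore the reasons for a null result. To say that a null result would be read as evidence against hand-washing goes beyond the text.

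**Conclusion.** The concern holds as a point about an unsupported assumption. The arithmetic at k = 0.3 is right, but k has no source, nothing larger is shown, there is no slack, and the team's own survey makes 0.3 look low. Over k of about 0.39 to 0.53, the 80% figure falls to about 60% down to 39%, and the 95% figure to about 82% down to 59%. It would be wrong to say that both figures fall to 40–60%: that range fits only the 40% reduction.

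The size rests on a k inferred from a range, on an assumed survey mean of 30% to 40%, on about 59 pupils per school, and on trial schools varying as the surveyed schools do. The documents do not establish that the trial is underpowered. They show that its stated power is unsupported, and that the team holds the data to settle the matter.

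**What to change.** Calculate k from the 34-school data, net of within-school sampling error and for the combined Ascaris and Trichuris prevalence that is the primary outcome. State its source. Restate the power and the detectable reduction in Sample size considerations and Table 1 at that k and over about 0.3 to 0.55. The cost is one recalculation and revised wording; the stated power may become less favourable.

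Where surveyed prevalence is available for the trial schools, consider stratifying the randomisation on it and adjusting for it in the analysis. The planned surveys are unlikely to serve this purpose: the baseline survey follows deworming, and the pre-deworming screen is described only for intervention schools. The downside is the loss of a few of the 14 degrees of freedom. Whether enough surveyed schools meet the water criterion is unknown, so this is an option to weigh and not a condition of the correction.
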